Dose Justification: Immunologic testing in mice indicates that there is no difference in antibody responses to P10s in mice between the 300 µg and 500 µg dose (GLP Report: “Determination of the Safety and Tolerability of Immunization with LeY Peptide Mimotope Vaccine in Mice”). Dose escalation is meant to test the safety of the preparation in terms of its non-immunological toxicity. In this case the assumption is that the putative adverse effects increase monotonically with the dose, and exploring the higher-than-necessary doses ensures safety of the lower ones. As for the immunological effects, they are characteristically non-monotonic with an optimal effect in a specific dose range, and weaker effects and even induction of tolerance for doses much higher or lower than the optimal one. Thus, the classical dose escalation trial may or may not detect the immunological effects, including adverse autoimmune phenomena. A dose-escalation algorithm better suited for determining the immunological impact should include both increasing and decreasing arms, and should be terminated when doses beyond the one that leads to optimal immunological effect are reached, provided they are tolerated otherwise. When increasing immunological effect is detected in one of the arms, the other one may be discontinued, if not necessary for the toxicology study.

4. Trial Objectives

a. Primary Objective – Safety: The safety and tolerability of the P10s-PADRE/ MONTANIDE™ ISA 51 VG vaccine will be determined by toxicity assessments throughout the duration of the study. Subjects will be evaluated for toxicity using the National Cancer Institute (NCI) Common Terminology Criteria for Adverse Events (CTCAE) Version 4.0. A toxicity of Grade 3 or higher will be considered a dose limiting toxicity (DLT).

b. Secondary Objectives – Immune Response:

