- 1) The effect of immunizing mimotope on the presence of circulating tumor cells (CTCs) will be determined by subjecting pre-and post-vaccination blood (drawn on weeks 0 and 21, respectively) to the RARE™ technique – a single-step negative enrichment process with a bispecific antibody directed against erythrocytes and CD45-positive cells (StemCell Technologies) (35-41). Determining the presence of CTCs prior to and following mimotope administration could provide a potential indicator for clinical disease (Müller V, Hayes DF, Pantel K. *Breast Cancer Res.* 2006;8(5):110). Though previous efforts to assay CTCs have had technical difficulties, we will use a simple protocol that requires only 7.5ml of blood, thereby decreasing the likelihood of technical complications.

5. Patient Population

Eligibility Criteria: Subjects are eligible for the vaccine study if the following inclusion and exclusion criteria are met:

- 1) Female subjects of all races with histologically or cytologically confirmed stage IV breast cancer are eligible. The cancer may be newly diagnosed metastatic or relapsed after primary or adjunctive therapy and must not have required a treatment change for 2 months. Treatments with anti-estrogen therapy or chemotherapy are allowed. The chemotherapy regimen cannot contain steroids in the pre or post supportive care medications. If a subject is on an investigational drug, the drug must be cleared from the body over a period of 4 weeks.
- 2) Disease staging will be done according to the American Joint Commission on Cancer (AJCC), sixth edition. The breast cancer staging information can be found at the following address:
<http://www.cancerstaging.org/education/tnmschema/breast.ppt>
- 3) Age 18 years and older of all races and ethnicity.
- 4) ECOG Performance Status 0 or 1.
- 5) Subjects must not have an active infection requiring treatment with antibiotics.
- 6) Subjects must not have other significant medical, surgical or psychiatric conditions, or require any medication or treatment, which may interfere with compliance of the treatment regimen.
- 7) Subjects must not have a diagnosis or evidence of organic brain syndrome, significant impairment of basal cognitive function or any psychiatric disorder that might preclude participation in the full protocol.

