- Toxicity evaluations using the NCI CTCAE (National Cancer Institute Common Terminology Criteria for Adverse Events) Version 4.0. Toxicities to be assessed are the laboratory parameters listed in the study calendar, as well as any sign or symptom found during the history and physical examination not noted at prestudy or on the baseline evaluation. Special attention will be paid to signs and symptoms related to injection reactions, injection site reactions or symptoms or laboratory findings indicating autoimmune toxicities.
- Concomitant medications will be collected from registration to end of treatment.

Week 2

- Administration of the P10s-PADRE/MONTANIDE™ ISA 51 VG vaccine. The vaccine will be administered subcutaneously (SC) by nurses in the Infusion Center at the Cancer Institute.
- Post vaccine administration, the following vital signs will be monitored every 15 (+/- 5 minutes) minutes for one hour: blood pressure, temperature, and pulse.
- Complete medical history and physical examination
- Complete blood count with differential
- Toxicity evaluations using the NCI CTCAE (National Cancer Institute Common Terminology Criteria for Adverse Events) Version 4.0. Toxicities to be assessed are the laboratory parameters listed in the study calendar, as well as any sign or symptom found during the history and physical examination not noted at prestudy or on the baseline evaluation. Special attention will be paid to signs and symptoms related to injection reactions, injection site reactions or symptoms or laboratory findings indicating autoimmune toxicities.
- Concomitant medications will be collected from registration to end of treatment.
- Collection of serum samples used to measure the immune response to the vaccine. If vaccine is given on these days, the study labs will be drawn before the vaccine is administered.

- Study lab samples. Up to 40 mLs of blood will be collected in red and purple tubes for circulating tumor cell evaluation, TACA (tumor associated carbohydrate antigens) assessment, and immune effector assays.

Week 3

- Administration of the study vaccine. The vaccine will be administered subcutaneously (SC) by nurses in the Infusion Center at the Cancer Institute.
- Post vaccine administration, the following vital signs will be monitored every 15 (+/- 5 minutes) minutes for one hour: blood pressure, temperature, and pulse.
- Complete medical history and physical examination
- Complete blood count with differential

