- f. **Dose Limiting Criteria:** Subjects who develop any grade 3 or greater toxicity as per NCI CTCAE v. 4 toxicity criteria, Grade 2 or greater autoimmune toxicity with the exception of vitiligo, or Grade 2 or greater hypersensitivity reactions will be treated and referred for additional care as indicated with systemic steroids, topical steroids, epinephrine or Benadryl. These subjects will be removed from the study and will be followed as per protocol defined monitoring and/or until resolution of toxicity.
- g. **Dose Assignment:** Subjects will be treated with vaccine admixed with MONTANIDE™ ISA 51 VG on weeks 1, 2, 3, 7 and 19 in cohorts according to the following dosing diagram:

DLT and the immune-response endpoints are defined in Section 4, “Trial Objectives”. Upon evaluation of all subjects in a cohort (3 or 6 per dose level), the decision whether to escalate, de-escalate or stop will proceed according to the cohort-appropriate schedule shown in **Tables 1, 2, and 3**.

Table 1: Toxicity Decision Rules for Initial Cohort (300 µg Vaccine Dose)

DLTs/ Cohort¹	Action
0/3	Begin accrual to Escalation Cohort
1/3	Expand Initial Cohort to 6 subjects
1/6	Begin accrual to Escalation Cohort
2/6, 3/6, or 4/6	Begin Accrual to De-Escalation Cohort
2/3 or 3/3	Begin Accrual to De-Escalation Cohort

¹ DLT = Dose-Limiting Toxicity

Table 2: Toxicity Decision Rules for Escalation Cohort (500 µg Vaccine Dose)

DLTs/ Cohort¹	Action
0/3 or 1/3	Expand cohort to 6 subjects
1/6	Stop: Declare escalation dose to be MTD ²
2/6, 3/6, or 4/6	Stop: Previous dose level is MTD ²
2/3 or 3/3	Stop: Previous dose level is MTD ²

¹ DLT = Dose-Limiting Toxicity² MTD = Maximum Tolerated Dose**Table 3: Toxicity Decision Rules for De-Escalation Cohort (100 µg Vaccine Dose)**

DLTs/ Cohort¹	Action
0/3 or 1/3	Expand cohort to 6 subjects.
1/6	Stop: De-escalation dose level is the MTD ²
2/6, 3/6, or 4/6	Stop: De-escalation dose level is above MTD ²
2/3 or 3/3	Stop: De-escalation dose level is above MTD ²

¹ DLT = Dose-Limiting Toxicity² MTD = Maximum Tolerated Dose

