If the initial-cohort dose of 300 µg P10s-PADRE is declared to be the MTD and only 3 subjects were enrolled into the initial cohort, then this cohort will be expanded to 6 to assure that 6 subjects are treated at the MTD. The CRA for the trial will assign the subjects to cohorts and communicate the assignments to the research nurse, who will communicate them to the investigator. Only one cohort will be open to enrollment at a time. After the last non-boost dose in each cohort, the study will have a 3-week hold pending the cohort's DLT evaluation. Staggered dosing for the first two patients within each cohort will allow an interval of one week observation for toxicity following the first injection in the previous patient. The research pharmacist will be notified by orders of the registration and cohort dose. Expansion of the cohort to 6, or enrollment to the next cohort, may start once the previous 3 subjects complete their week-9 serology and are evaluated for DLT. Subjects who withdraw from the dose-escalation study without a DLT will be replaced. Subjects who withdraw from the dose- de-escalation study without a DLT will be replaced. Subjects who withdraw with a DLT will be considered evaluable for MTD determination.

8. Risks and Toxicities To Be Monitored

a. Potential Toxicities, Risks and Precautions:

Procedure	Risks	Measures to Minimize Risks
Complete history and physical exam, including blood chemistries	Identification of previously unknown condition	Qualified health care provider to evaluate potential subject Research records are kept in a locked area accessible only by study personnel.

Procedure	Risks	Measures to Minimize Risks

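### The DLT rule has no attribution step, so a Grade 3+ event clearly caused by chemotherapy or progression counts in Tables 1-3 and ends that woman's vaccination

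*Combined protocol and SAP*

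**What the plan says.** Section 4.a defines a DLT by grade (3 or higher). Section 7.f applies to "Subjects who develop any grade 3 or greater toxicity as per NCI CTCAE v. 4 toxicity criteria", and adds Grade 2+ autoimmune toxicity (except vitiligo) and Grade 2+ hypersensitivity. Section 11 makes every event that meets those criteria a DLT, and Section 12.b scores it so. None of the four mentions cause.

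The visit text in Section 7.d defines what is assessed: the calendar laboratory values, plus "any sign or symptom found during the history and physical examination not noted at prestudy or on the baseline evaluation". That filters signs and symptoms by timing, not by cause.

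The women have stage IV breast cancer, and eligibility criterion 1 in Section 5 adds: "Treatments with anti-estrogen therapy or chemotherapy are allowed".

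A DLT has two consequences. It enters Tables 1-3, and women who withdraw with one stay evaluable for the MTD (Sections 7.g and 12.a). It also ends participation: "These subjects will be removed from the study and will be followed as per protocol defined monitoring and/or until resolution of toxicity". A paragraph in Section 8 repeats the removal and stops the injections.

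Attribution does appear elsewhere. Section 16 asks for a relatedness judgement on the CRF, and Section 17.b.5 limits its rules on three SAEs and two Grade 4 toxicities to events linked to the study product.

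**The concern.** Read as written, a Grade 3+ cytopenia plainly caused by chemotherapy, or a Grade 3+ symptom plainly caused by progression, is a vaccine DLT. Progression itself is not named as one; the point is the graded signs, symptoms and laboratory values that it produces.

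Tables 1-3 turn on single events in cohorts of three to six. Events unrelated to vaccine dose can lower the declared MTD or open the 100 µg cohort, where they are just as likely to recur. Stopping at 300 µg is a limited loss, since Section 3 reports no difference in mouse antibody response between 300 and 500 µg. De-escalation matters more, and so does each woman who loses remaining doses for an event the vaccine did not cause. An event after Week 9 would not normally move the tables, but would still cost her the Week 19 booster. The removal sentence also leaves open whether her later titers are collected.

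**Working it through.** **The plan's own figure.** With no DLTs, Table 1 uses 3 women and Table 2 expands to 6: 3 + 6 = 9, as Section 12.a states.

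**Inputs.** From the documents: Tables 1-3, the 9-week DLT window, and the Section 7.g rule that expands 300 µg to six women if it becomes the MTD after only three. Assumed: independent women; 0/6, which Tables 2 and 3 do not list, treated like 1/6; and a background Grade 3+ rate q over 9 weeks of 5, 10, 15 or 20%. Eligibility should keep q low: two months without a treatment change, ECOG 0-1, laboratory limits, no active infection, no CNS metastases.

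**Effect on dose decisions, no vaccine DLTs (p = q).**
- 500 µg opens: O(p) = (1-p)^3 + 3p(1-p)^5
- At most 1/6: L(p) = (1-p)^6 + 6p(1-p)^5
- 500 µg clears = O × L; ends at 300 µg = O × (1-L); de-escalates = 1-O

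At q = 0.10: O = 0.729 + 0.177 = 0.906 and L = 0.531 + 0.354 = 0.886. So 500 µg clears with 0.803, the trial ends at 300 µg with 0.104, and it de-escalates with 0.094.

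| q | 500 µg clears | ends at 300 µg | de-escalates | clears, quarter of background excluded (p = 0.75q) | clears, half excluded (p = 0.5q) |
|---|---|---|---|---|---|
| 5% | 94% | 3% | 3% | 97% | 98% |
| 10% | 80% | 10% | 9% | 88% | 94% |
| 15% | 63% | 18% | 19% | 76% | 88% |
| 20% | 46% | 24% | 29% | 63% | 80% |

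**Women removed for a clearly non-vaccine event.** Let a be the share of background events that are clearly attributable to another cause. On the nine-woman path alone the chance of at least one is roughly 1-(1-aq)^9; for a = 0.5 and q = 0.05 that is 1-0.975^9 = 0.204. Summing exactly over all paths, including the extra women enrolled on expansion or de-escalation, gives for q = 5/10/15/20%:
- a = 0.5: 21/38/53/65%
- a = 0.25: 11/22/32/41%

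These count events in the 9-week windows only.

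**Price of an attribution step.** Assume true vaccine DLT rates v of 20% at 300 µg and 33% at 500 µg, a share e of background excluded, and a share m of vaccine events wrongly excluded. Then p = 1-(1-v(1-m))(1-q(1-e)), and 500 µg is declared the MTD with probability O(p at 300) × L(p at 500). As written at q = 0.10: p = 0.280 and 0.397, giving 0.536 × 0.238 = 0.128.

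| q | as written | e = 0.5, m = 0 | m = 10% | m = 20% |
|---|---|---|---|---|
| 5% | 18% | 22% | 28% | 34% |
| 10% | 13% | 18% | 23% | 29% |

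With no background events and no misjudgement the same tables give 0.709 × 0.358 = 25%.

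**The case against.** The strongest reply is that this is a consistent, conservative rule for a first use in humans. Grade-only counting appears in four places, and Section 17.b.5 shows that the authors wrote attribution in where they wanted it. The Medical Monitor reviews all toxicities (Section 8.a), and the team meets after each cohort and may make adjustments (Section 17.b.4). All of that is fair, but no sentence says that all-cause counting is intended, and none lets the team set aside a plainly unrelated event when counting DLTs.

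The size objection largely stands. At 5% background, excluding a quarter to a half of events gains only 2 to 4 points in clearing 500 µg. If 10-20% of vaccine events are misjudged, the chance of declaring a toxic 500 µg the MTD rises by about 9 to 16 points. At 10% background the gain with half excluded is 14 points, against an added risk of 6, 11 or 17 points at 0, 10 or 20% misjudged. A lower as-written risk than the 25% no-background figure reflects background events added to the count, not better detection of vaccine toxicity. Results above 25% do reflect misjudgement.

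A reader might infer three stronger things that the documents do not support:
- That the rule contradicts Section 3, where "the assumption is that the putative adverse effects increase monotonically with the dose". A constant background plus a rising vaccine effect still rises with dose. Section 3 also wants a decreasing arm, so 100 µg data are not worthless.
- That an unrelated Grade 3+ illness is irresolvably either a DLT or a replaceable withdrawal, because Section 8 lists unrelated illness separately and Section 7.g says "Subjects who withdraw from the dose-escalation study without a DLT will be replaced". Section 11 settles the literal reading: it is a DLT.
- That a woman is wrongly removed with probability 37/61/77/87%, from 1-(1-q)^9. That treats every background event as clearly attributable. Hematologic toxicity is a listed vaccine risk and raised hepatic enzymes a listed adjuvant risk, so many such events should go on counting.

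**Conclusion.** The point holds in limited form. The stated rule gives the wrong answer for one class of event: Grade 3+ events clearly due to chemotherapy, progression or another identified cause. The MTD effect is small at an assumed 5% background and material only from about 10%; nothing in the documents supports or excludes 15-20%. The more likely harm is to individual women, at 21/38/53/65% or 11/22/32/41% depending on whether half or a quarter of background events are clearly attributable. Not all of that lost vaccination is due to the DLT rule, because Section 8 also allows termination for unrelated illness, declining performance status or the investigator's judgement.

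This should be changed, but it does not show that the trial would reach the wrong dose, nor that attribution is free of risk. The figures rest on independence, a background rate unrelated to dose, and reading 0/6 as 1/6.

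**What to change.** In Sections 4.a and 7.f: a Grade 3+ event is a DLT unless the Medical Monitor and PI document, before the cohort count, that it is clearly due to progression, concurrent anticancer therapy or another identified cause. Possible, probable and unresolved events count. Grade 2+ autoimmune (except vitiligo) and Grade 2+ hypersensitivity events always count.

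Hold vaccination while the decision is pending, and apply the removal sentences in 7.f and Section 8 only to confirmed DLTs. A woman with an excluded event stays evaluable if she completes Week 9; otherwise she is replaced. In 12.b, report all-cause and attributed Grade 3+ counts side by side by cohort. If all-cause counting is in fact intended, say so in 7.f and still report both.

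The cost is a few sentences in one amendment. Relatedness is already requested on the CRF (Section 16), and the Medical Monitor already meets the team before the next cohort opens (Section 17.a). The added work is a decision before a held dose; because visits have a ±3-day window, the amendment should say whether a delayed dose is given late or skipped. It should also state the misjudgement risk, which is the reason to confine the exclusion to clear, documented causes.

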Administration of study vaccine	
Experimental agent may be toxic or harmful.
 
First time use in humans
 
Risk of local reactions (i.e. swelling, redness, tenderness, itching, extravasations)
 
Potential for side effects ranging from hematologic toxicities and hypersensitivity reactions to anaphylaxis
 
Unanticipated risks
 
Unknown risks
	
Careful monitoring by clinic visits and 24 hour, 7 days per week physicians on call for unexpected problems
 
Only non-pregnant, non-lactating females may participate. The use of contraception during the study and the use of contraception for 18 months post completion of the trial are required.
 
Frequent laboratory tests including complete blood count (CBC) with differential, liver function tests, etc.
 
Close and frequent monitoring of subjects by qualified staff
 
DTH assay to monitor for hypersensitivity reactions
 
Emergency equipment including crash carts, advanced cardiac life support (ACLS) certified staff and rescue medications such as Benadryl, epinephrine, high dose steroids, etc. will be on-site during administration.
 
The Medical Monitor will review all toxicities on a regular basis and will be available to aid subjects as needed.
 
The study drug may be discontinued.
 
This research is being conducted at an experienced clinical research center.
 
Reporting and monitoring mechanisms are in place for AEs, serious adverse events (SAEs) and unanticipated problems.

Administration of MONTANIDE™ ISA 51 VG	
Dermatology/Skin: local erythema, rash, pruritis
 
Gastrointestinal: diarrhea, anorexia, nausea, vomiting, abnormal taste
 
Hepatic: elevated
	
Careful monitoring by clinic visits and 24 hour, 7 days per week physicians on call for unexpected problems
 
Only non-pregnant, non-lactating females may participate. The use of contraception during the study and the use of contraception for 18 months post completion of the trial are required.

Procedure	Risks	Measures to Minimize Risks

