Subjects will receive up to 5 planned vaccine doses unless they withdraw from the study or develop a dose limiting event as stated above, at which time they will discontinue the injections and be removed from the study. There will be no dose modifications for toxicity. Special attention will be given to toxicities mediated by autoimmune mechanisms, such as colitis, thyroiditis or systemic lupus erythematosus (SLE), as well as to injection-site local reactions or allergic reactions. The NCI CTCAE Version 4.0 will be used for toxicity and SAE reporting. A copy of the CTCAE Version 4.0 can be downloaded from the Cancer Therapy Evaluation Program (CTEP) home page or viewed in **APPENDIX A**. All appropriate treatment areas have access to a copy of the CTCAE Version 4.0.

Any subject may voluntarily revoke consent and withdraw from the study at any time. A subject may be terminated early for the following conditions: (i) non-compliance, (ii) an unrelated intercurrent illness that may affect assessment or place the subject at risk for AEs or require systemic steroids, (iii) deterioration in performance status so as to make participation a hardship for the subject, (iv) for toxicity as determined by the DLT criteria, or (v) for any reason that the investigator feels it is not in the subject's best interest to continue.

- b. Benefits:** As this is the first time Mimotope P10s-PADRE will be administered to humans, there are no clearly defined benefits to subjects of this study. However, this vaccine may potentiate an immune response which could improve median progression-free survival and overall survival of cancer patients.
- c. Injury:** For DOD-funded research, participants can receive medical care at an Army hospital or clinic free of charge. If participants pay out-of-pocket for medical care elsewhere for injuries caused by this research study, they should contact the Principal Investigator. If the issue cannot be resolved, contact the U.S. Army Medical Research and Materiel Command (USAMRMC) Office of the Staff Judge Advocate (legal office) at [contact]/[name]

9. Specimen Handling

Samples will be stored in the UAMS Tissue Procurement Facility, located in room B.018 of the hospital. Cryotubes that contain specimens will be labeled with barcodes. The coded number is linked to patient identification and time of blood draw. Specimens will be stored frozen at -80°C

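### A second DLT already settles that a dose level has failed, yet it triggers no hold of its own: apart from the Section 17.b.5 stops and a late three-week hold, enrolment, replacement and dosing at that level continue by default

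*Combined protocol and SAP*

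**What the plan says.** **When the tables act.** Section 7.g: "Upon evaluation of all subjects in a cohort (3 or 6 per dose level), the decision whether to escalate, de-escalate or stop will proceed" by the table for that cohort. Section 12.a repeats this and puts DLT assessment at nine weeks per subject.

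**What the tables do.** In each of Tables 1 to 3, the rows 2/3 or 3/3 and 2/6, 3/6 or 4/6 carry one failing action: de-escalate from 300 µg, take the previous level as MTD at 500 µg, or declare 100 µg above the MTD.

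**What counts as a DLT.** Section 7.f names any Grade 3 or higher toxicity, "Grade 2 or greater autoimmune toxicity with the exception of vitiligo, or Grade 2 or greater hypersensitivity reactions". Section 11 makes any event meeting these criteria a DLT.

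**What goes on meanwhile.** Section 12.a lets the second and third subjects of a cohort enter before the first has finished her injections. Section 8: "Subjects will receive up to 5 planned vaccine doses unless they withdraw from the study or develop a dose limiting event as stated above". Section 7.g: "Subjects who withdraw from the dose-escalation study without a DLT will be replaced", with the same sentence for de-escalation.

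**What can interrupt it.**
- Section 7.g: "Expansion of the cohort to 6, or enrollment to the next cohort, may start once the previous 3 subjects complete their week-9 serology"; their DLT assessment must be done as well.
- Section 7.g: "After the last non-boost dose in each cohort, the study will have a 3-week hold pending" (the wait is for DLT results in that cohort).
- Section 17.b.5: the study stops for a death not due to cancer or two related Grade 4 toxicities, and is suspended at three attributed SAEs.
- Discretionary: Section 8.a says "The Medical Monitor will review all toxicities on a regular basis" and that the drug may be discontinued; Section 8 clause (v) lets the investigator end a subject's participation; Section 17.a has a safety meeting between cohorts.

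Section 7.g also says subjects are treated "in cohorts according to the following dosing diagram". That diagram is not in the available text.

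**The concern.** Once two DLTs have occurred within the nine-week windows, no later observation in the cohort can alter the dose decision. Further injections at that level add exposure without informing the choice of dose. The written rules nevertheless keep enrolling, dosing and replacing until the last subject is evaluated.

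This is a first-in-human vaccine for which Section 8.b says there is no clearly defined benefit to subjects. A pause for review costs little. Without one, women may be vaccinated, or newly enrolled, at a level that has already failed.

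**Working it through.** **1. The plan's own figures.** Two subjects a month is one every 52/24 = 2.17 weeks. Three subjects take 2 × 2.17 + 9 = 13.3 weeks, matching the stated 13. With no DLTs, 3 + 6 = 9 subjects, as stated.

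**2. Does the second DLT fix the action?** In the first three subjects, two DLTs leave only 2/3 or 3/3. Expansion is reached only from 0/3 or 1/3, so the total cannot exceed 4/6, and two or more means 2/6, 3/6 or 4/6. These rows share one action in every table, so yes.

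**3. Does any rule then require a pause?**

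| Provision | Triggered by two Grade 3 DLTs, or two Grade 2 autoimmune or hypersensitivity DLTs? |
|---|---|
| Section 17.b.5 stop or suspension | Only if its own terms (death, Grade 4, three attributed SAEs) are also met |
| Three-week hold (7.g) | Not triggered by them; applies at any grade, but only after the cohort's last non-boost dose |
| No expansion or next cohort before week 9 (7.g) | Does not stop enrolment or dosing within the block of three |
| Medical Monitor review, discontinuation, clause (v) | Permitted, not required |

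**4. Calendar at the stated accrual, in weeks from the first subject's first injection.**
- First block: enrolment at 0, 2.2 and 4.3; verdict at 13.3.
- Expansion (assumed to open at that verdict): enrolment at 13.3, 15.5 and 17.7; verdict at 17.7 + 9 = 26.7.
- Boosters come 18 weeks after the first injection: 18.0, 20.2 and 22.3 for the first three subjects.
- In an expanded cohort the three-week hold runs from 17.7 + 6 = 23.7 to 26.7.

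So no booster falls while a three-subject verdict is pending. In an expanded cohort all three first-block boosters fall before both the hold and the verdict. The hold begins after the last primary injection, so it prevents none of them.

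**5. Chance that a level fails (exact binomial; DLT rate p assumed).**
- Table 1: P(at least 2 of 3) + P(1 of 3) × P(at least 1 of 3). At 20%: 0.104 + 0.384 × 0.488 = 0.291.
- Tables 2 and 3 add P(0 of 3) × P(at least 2 of 3). At 20%: 0.291 + 0.512 × 0.104 = 0.345.

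| p | 5% | 10% | 20% | 33% | 50% |
|---|---|---|---|---|---|
| Table 1 | 0.03 | 0.09 | 0.29 | 0.57 | 0.83 |
| Tables 2–3 | 0.03 | 0.11 | 0.34 | 0.64 | 0.89 |

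**6. Exposure after the second DLT.** Simulation, 30,000 trials per setting: calendar as in step 4, injections at 0, 1, 2 and 6 weeks, no withdrawals, Section 17 stops not modelled. Table 1, p = 20%, given failure:

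| Assumed DLT onset | Primary-series injections | A new subject may enrol | Weeks to verdict |
|---|---|---|---|
| Uniform over 9 weeks | 2.0 | 20% | 6.3 |
| Within 7 days of any of the 4 injections | 3.0 | 37% | 8.0 |
| Within 7 days of the first 3 | 3.7 | 52% | 9.4 |
| In the 3 weeks after the Week-7 injection | 0.7 | 0% | 3.4 |

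Per cohort opened, multiply by 0.291: 0.7 gives 0.2, 3.7 gives 1.1, and 52% gives 15%. At p = 10% the primary-series range per cohort opened is 0.07 to 0.36. Ending the window eight weeks after the first injection, with the first two onset patterns and rates of 20% to 50%, gives 1.8 to 2.9 per failed cohort over all three tables.

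**7. Boosters still due at a failing 300 µg verdict.** These belong to DLT-free subjects in the last block of three. At p = 20%: 0.096 × 1 + 0.384 × (0.384 × 2 + 0.096 × 1) = 0.43 per cohort opened, and 0.43 / 0.291 = 1.5 per failed cohort (0.7 if half of them reach Week 19).

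**8. Largest case without replacements.** After 1/3, a DLT in subject 4 within a week of her first injection (week 14.3) fixes 2/6. Subjects 5 and 6 may still enrol (8 primary-series injections), and four DLT-free subjects may still be boosted, up to 12 injections in all. The verdict comes 26.7 − 14.3 = 12.4 weeks later.

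**9. Replacement.** If 10% to 20% of subjects withdraw within their nine weeks (assumed), the text calls for a replacement after the second DLT in 4% to 21% of failed 300 µg cohorts at p = 20%. Each could add up to five injections.

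**The case against.** The strongest reply is that the plan is not silent. Two related Grade 4 toxicities or a death not due to cancer stop the study, three attributed SAEs suspend it, and the three-week hold applies at any grade if the second DLT falls inside it. A reader might infer that nothing in the plan ever requires a pause; the documents do not support that. What stands is narrower: none of these provisions is triggered by the second DLT as such, and the two Grade 3, or Grade 2 autoimmune or hypersensitivity, cases can miss them all.

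A reader might also infer that boosters would certainly continue at a failed 500 or 100 µg dose. Failing rows in Tables 2 and 3 begin with Stop, but so does the passing 1/6 row, so the booster's status there is ambiguous. The post-verdict booster point is therefore made only for 300 µg. Even there, if the first three subjects fail and the next cohort opens at once, the Section 17.a meeting precedes every booster.

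Continued dosing is mostly permitted rather than compelled, although replacement is worded as mandatory. DLTs need no attribution, chemotherapy is allowed, and booster response is a secondary objective, so resuming can be right for some women. That argues for suspension with review rather than irrevocable closure. Finally, the dosing diagram was not seen, so a hold shown there cannot be excluded.

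**Conclusion.** The point holds in this limited form: the second DLT fixes the failing action, the tables wait for full evaluation, and no sentence in the available text ties a hold to that event beyond the Section 17.b.5 rules and the late three-week hold. The default continuation covers enrolment within the cohort, replacement, the remaining primary series and, in an expanded cohort or after a failing 300 µg verdict, the Week-19 booster.

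The size is modest per cohort opened and larger once a cohort fails. All exposure figures rest on assumed DLT rates and onset patterns; the documents give neither. The top of the range needs every DLT to fall within a week of one of the first three injections. The MTD decision itself is not affected. This is a cheap patient-safety improvement; confidence is medium because of the unseen diagram.

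**What to change.** Add to Sections 7.g, 12.a and 8:

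> When a second DLT is observed at a dose level within its subjects' 9-week DLT windows, enrolment, replacement and all further injections at that level, including the Week-19 booster, are suspended at once pending prompt Medical Monitor and PI review. If both DLTs are confirmed, enrolment and replacement at that level close and the failing table action applies; a DLT-free subject may resume injections only with documented case-by-case approval and after she is told of the finding. If a DLT is not confirmed, enrolment, replacement and dosing resume. Safety follow-up continues, and the next cohort, or expansion of the previous one, still waits for the enrolled subjects' week-9 evaluation and the Medical Monitor meeting. DLTs after the 9-week window do not change the table count but are referred promptly to the Medical Monitor.

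Tables 1 to 3 stay as they are. Suspension rather than closure matters because Section 12.c allows data to be corrected at source. The nine-week limit matters because, if booster DLTs counted, a 1/6 pass with five boosted subjects would turn into a failure with probability 1 − (1 − q)^5, which is 0.10, 0.23 or 0.41 for assumed booster DLT rates q of 2%, 5% or 10%.

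Cost: one paragraph in an amendment. Some booster and titer data are lost at a dose that failed. A failed cohort may close with fewer subjects, so its DLT proportion has a smaller denominator and the titer medians planned for cohorts of six may not be produced. Dosing may pause briefly for DLTs unrelated to the vaccine.
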